5.9 Corelabs

All blood laboratory testing will be performed at Quest Diagnostics. Quest will provide uniform collection materials, sample pick-up, and sample storage. The use of a central core laboratory is expected to provide reliable and accurate blood tests and a mechanism for monitoring adherence.

6.0 Assessment of A-Tube Technical Success

Technical success is defined as successful endoscopic placement of a functional A-Tube and installation of a functional Skin-Port.

7.0 Assessment of safety

7.1 Risk Assessment

There risks of this study may be categorized into those associated with (i) endoscopic placement of the A-Tube, (ii) the presence of stomas/fistulas and A-Tube, (iii) Aspiration Therapy, (iv) behavior, and (v) concomitant drug therapy.

Each of these risk categories and the associated mitigations are discussed in **Sections 7.1.1 -7.1.5**.

7.1.1 Risks Associated with Endoscopic Placement

The risks of endoscopic placement of the A-Tube include sedation complications, discomfort, sore throat, pain, abdominal bloating, indigestion, bleeding, infection, nausea, vomiting, hypoventilation, aspiration pneumonia, perforation, and death.

The risk of infection is mitigated by the use of prophylactic antibiotics before and after the endoscopic procedure. The risk of sedation complications and aspiration pneumonia are mitigated by having the endoscopic procedure performed by a skilled and experienced medical team, who will carefully monitor the subject. The risk of perforation is mitigated by having endoscopic procedure performed by a trained endoscopist who is experienced in inserting PEG tubes. The risk of death is mitigated by all the above.

7.1.2 Risks Associated with Stomas/ Fistulas and A-Tube

Risks related having a fistula/ stoma include: 1) abdominal discomfort/pain, 2) peristomal skin irritation/ inflammation, erythema and granulation tissue formation, 3) peristomal leakage and/or bleeding, 4) infection, 5) buried bumper syndrome and gastric erosion, 6) difficulty sleeping on abdomen,

reduced range of motion at the torso, 7) persistent fistula after tube removal, and 8) scarring and/or skin depression after tube removal.

Abdominal Discomfort/Pain. It is normal for subjects to have abdominal discomfort after endoscopic A-tube (or PEG tube) insertion, which subsides over several weeks. Subjects will be instructed to take over-the-counter pain medications such as acetaminophen as needed for 1 week after A-Tube placement. In addition, at discharge from the endoscopy suite, subjects will be given a 1-week prescription for pain medications that can be used to control abdominal discomfort. Supplementary pain medication will also be provided at the physician's discretion. The experience from the Feasibility Study found that musculoskeletal or neuropathic complaints (e.g. burning, pulling) after tube placement was effectively treated with general oral pain medications and/or medications for neuropathic pain. It was thought by the Sponsor and the Study Team that discomfort after the first few weeks was primarily associated with the "old" A-Tube design (e.g., ePTFE tube with helical ridges of exterior or tube). With the new A-Tube design implemented in September 2011, subjects report significantly greater comfort.

Peristomal Skin Irritation, erythema, discharge and granulation tissue. Based upon our studies to date, skin irritation, erythema, discharge and granulation tissue formation are common, minor, and manageable, and most subjects reported at least one such complication. After the new A-Tube design was implemented in September 2011, subjects reported a marked decrease in discharge and greater comfort. Skin irritation and erythema can be treated with topical zinc oxide, or other topical creams/products and by making sure the Skin-Port is ~1 cm away from the skin to reduce irritation. It is normal for granulation tissue to form at the ostomy site of the A-Tube. If the granulation tissue is excessive, it is easily removed by topical application with silver nitrate sticks. The area should be swabbed with alcohol before and after treatment. Care should be taken to ensure that silver nitrate does not come into direct contact with normal skin tissue, fistula track, or A-Tube. In addition, subjects are taught to inspect their stomas and report any evidence of irritation, erythema, discharge and granulation tissue. clinical team is also instructed to examine the stoma at every visit, and treat, as necessary.

Peristomal leakage. Leakage can be caused by the tube by (i) failure of the stomach stoma to heal around the tube, (ii) enlargement of the stomach stoma (sometimes caused by an infection within the tract or mechanical forces from

excessive tube manipulation), or (iii) buried bumper syndrome. The tube should be checked to make sure it can move freely in and out within the fistula tract to rule out the possibility of a buried bumper. If there is no evidence of a buried bumper, the patient should be instructed (i) not to aspirate and (ii) to avoid any manipulation of the tube to allow the stomach stoma to heal and form a tight seal. If skin irritation or excoriation occurs, skin care recommended for peristomal irritation can be started. If leakage persists after seven days, the A-Tube can be removed for several days and the tract allowed to partially close. A new A-Tube can then be placed through the same site.

Infection. The use of prophylactic antibiotics has markedly reduced the risk of bacterial infection after PEG tube insertions. If an infection occurs at the A-Tube site, it can usually be successfully treated as an outpatient: oral antibiotics for a bacterial infection or topical cream/oral antifungal agent for a fungal infection.

Buried Bumper. Buried bumper syndrome is a known complication of PEG tubes⁵⁹ that occurs when there is excess tension of the internal bumper against the intragastric wall, which causes migration of the internal bumper into the fistula tract. In the clinical studies to date, there was one such incidence of a buried bumper, which was caused by inappropriate shortening of the A-tube. The clinical team is instructed to determine Skin-Port placement when the subject's abdomen in compressed (seated) to ensure sufficient clearance (~3-10mm) between the Skin-Port and the abdominal wall. Additionally, subjects are instructed to avoid external tension on the Skin Port and to call the physician if the Skin Port feels tight against the abdominal wall.

Persistent Fistula after A-Tube Removal. Although the majority of fistulas close within a few days after tube removal, some subjects will require endoscopic or surgical closure if the fistula does not heal on its own.

Scarring after A-Tube Removal. Removal of the A-tube and fistula closure will result in a scar and skin indentation on the abdominal wall at the ostomy site.

7.1.3 Risk Associated with Aspiration Therapy

Some subjects in the Pilot and Feasibility Trials reported occasional indigestion, nausea, vomiting, constipation, and diarrhea as a result of

aspiration. Subjects may experience discomfort and/or pain when attaching the Connector to the Skin-Port for aspiration within the first several weeks after A-Tube placement, however, this subsides as the stoma tract heals. All of these reported incidents were mild in nature and fleeting.

The nutritional and metabolic risks related to Aspiration Therapy include hypokalemia, and iron (Fe) deficiency anemia.

Nutritional and Metabolic Risks

Hypokalemia. A decrease in plasma potassium concentration can occur with repeated aspiration of gastric contents, because of the loss of gastric acid and compensatory potassium bicarbonate excretion by the kidney. Plasma potassium concentrations will be closely monitored in study subjects and appropriate therapy will be initiated if plasma potassium concentration begins to decline.

Iron deficiency anemia. Serum Fe decreased in several subjects treated with Aspiration Therapy in the Feasibility Study. Several mechanisms could be responsible for the decline in serum Fe: 1) reduced dietary iron availability because of the decrease in total food intake and the aspiration of a portion of gastric contents after meal (iron) ingestion, 2) adherence with a low calorie diet and weight loss itself is associated with a decline in serum Fe; data from previous weight loss studies have found that a low-calorie diet can cause a marked reduction in serum Fe concentration within 2-4 weeks⁶⁰, 3) increased iron loss caused by increased menstruation, which often occurs with weight loss in obese women⁶¹. The decrease in serum Fe was associated with a decrease in hemoglobin concentration, with the development of anemia in a few subjects. Short-term treatment with iron supplementation resulted in a return of serum Fe to the normal range and was associated with an increase in hemoglobin concentration.

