The incidence of procedure-related, device-related, and therapy-related adverse events will be measured, as well as the incidence of device related, or unrelated, serious adverse events, including unanticipated adverse device effects. Also, the development of adverse eating behaviors will be assessed.

Schedule of Assessments:

The Schedule of Assessments for the Control Group and the AT group are shown in **Tables 1-3**.

Table 1: Schedule of Assessments, Year 1-AT Group

YEAR 1	Screen	lom		Da	ay		Week of Therapy															
Visit	Screen	Random	0	1	7	14	0	0.5**	2	6	10	14	20	24	28	32	36	40	44	48	52	Total
Visit window (+ days)			0	0	1	4	2	1	2	7	7	7	7	7	7	7	7	7	7	7	7	
Informed consent	Х																					1
Screening interview	Х																					1
Medical History & Physical Exam	х																				х	2
EKG	х																				х	2
IWQOL	х																				х	2
Questionnaire on Eating and Weight Patterns (QEWP)	х											х			Х						х	4
Eating Disorders Examination (EDE)	х											х			х						х	4
Randomization phone call		х																				1
A-Tube placement			х																			1
Skin-Port placement, Aspiration training, Initiate treatment						х																1
Phone check (RC or RN)				х			х															2
MD visit					х							х			х						х	4
Medical & Study Visit (weight, vital signs, concom meds, med																						16
adherence, AE's)					Х	х		X	Х	Х	Х	х	х	х	Х	Х	Х	Х	х	Х	Х	16
Initial body weights	х		x*																			2
Dietary Evaluation					х																	1
Lifestyle Therapy						х			х	х	х	х	х		х		х		х		х	10
Height	х																					1
Urine pregnancy	х																					1
Urine protein (dipstick)						х		х	х	х	х	х	х		х		х		х		х	11
Electrolyte panel+ magnesium + calcium								х	х	х	х	х	х				х		х			8
CMP + Magnesium	х														Х						х	3
CBC	х																				х	2
Hemoglobin & hematocrit												х			х							2
PT/PTT	х																					1
TSH	х																					1
Lipid Panel	х														х						х	3
Iron	х											х			х						х	4
Vitamin D 25-OH	х																				х	2
Hemoglobin A1C	х											х			х						х	4
DEXA	х																				х	2
Subject photograph			х																		х	2
Town Hall meetings***		•	•	•							I	Every	other	mon	th aft	er 3 A	AT gro	oup st	ıbject	s are	enroll	ed
A-Tube shortening																	reede	_				

Table 2: Schedule of Assessments, Years 2-5-AT

YEARS 2-5								Week	of Th	ierapy	7							

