Visit	60	68	76	90	104	117	130	143	156	169	182	195	208	221	234	247	260	Total
Visit Window (+ days)	7	7	7	7	7	7	7	7	7	7	7	7	7	7	7	7	7	
Physical Examination					Х				х				х				х	4
EKG					Х				Х				Х				Х	4
IWQOL					х				Х				х				х	4
Questionnaire on Eating and Weight Patterns					х				Х				х				х	4
MD visit			х		х		х		х		х		х		х		Х	8
Medical & Study Visit (weight, vital signs,	x	х	v	х	х	х	v	v	Х	х	х	х	х	v	х	х	v	17
concom meds, med adherence, AE's)	^	^	Х	^	^	Α	Х	Х	Α .	^	^	^	Λ	Х	^	^	Х	17
Urine, Pregnancy																		0
Electrolyte panel + magnesium + calcium	х	х	х	х		х	Х	Х		Х	Х	Х		Х	Х	Х		13
CMP+ magnesium					Х				х				Х				Х	4
CBC					Х				Х				х				Х	4
Hemoglobin & hematocrit			х				Х				Х				Х			4
Lipid Panel					Х				х				х				х	4
Hemoglobin A1C			х		х		х		Х		х		х		х		х	8
Iron					Х				х				Х				Х	4
Vitamin D 25-OH					Х				х				х				х	4
DEXA					Х				х				х				х	4
Town Hall meetings***								Ev	ery of	ther n	onth							
A-Tube shortening									As 1	neede	d							
A-Tube replacement	As needed																	
A-Tube removal	11 .1				11					neede								

CMP: glucose, calcium, sodium, potassium, chloride, CO2, BUN, creatinine, albumin, total protein, alkaline phosphatase, ALT, AST, bilirubin +magnesium

 $\textbf{Electrolyte panel:} \ sodium, \ potassium, \ chloride, \ and \ CO_2 + magnesium + calcium$

Lipid panel: Total cholesterol, LDL-C, HDL-C, Triglycerides

 $\pmb{CBC:} \ hemoglobin, \ hematocrit, \ red\ blood\ cell\ count, \ white\ blood\ cell\ count\ and\ differential,\ \pmb{MCV:} \ mean\ corpuscular\ volume;\ \pmb{MCH:} \ mean\ corpuscular\ hemoglobin$

MCHC: mean corpuscular hemoglobin concentration, platelet count

*Day 0 weight should be obtained on same scale used during the study

** Week 0.5 denotes 48-72 hours after AT initiation

***Town Hall meetings shall begin after 3 subjects are enrolled

Table 3: Schedule of Assessments, Control Group

YEAR 1	Screen	Rai						W	eek of	Thera	ару						
Visit	screen	Random	0	2	6	10	14	20	24	28	32	36	40	44	48	52	Total
Visit window (+ days)			0	2	7	7	7	7	7	7	7	7	7	7	7	7	
Informed consent	Х																1
Screening interview	х																1
Medical History & Physical Exam	Х															х	2
EKG	Х															x	2
IWQOL	х															Х	2
Questionnaire on Eating and Weight Patterns (QEWP)	Х									Х						Х	3
Eating Disorders Examination (EDE)	х									х						х	3
Randomization call		х															1
MD visit			Х				Х			Х						х	4

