Medical & Study Visit (weight, vital signs, concom meds, med adherence, AE's)			х	х	х	х	х	х	х	х	х	x	x	х	x	х	14
Phone check (RC or RN)																	0
Dietary Evaluation			Х														1
Lifestyle Therapy			Х	х	х	Х	Х	Х		Х		х		Х		Х	10
Height	Х																1
Urine pregnancy	Х																1
Urine protein (dipstick)	Х			х	х	Х	х	Х		Х		х		Х		Х	10
Electrolyte panel+ magnesium + calcium				х	х	Х	х	Х				х		Х			7
CMP +Magnesium	Х									Х						Х	3
CBC	Х															Х	2
Hemoglobin & hematocrit							х			х							2
PT/PTT	Х																1
TSH	х																1
Lipid Panel	х									х						х	3
Iron	х																1
Hemoglobin A1C	х						х			х						х	4
Vitamin D 25-OH	Х																1
DEXA	х																1
Town Hall Meetings											Eve	ery othe	er mon	th			

Table of Acronyms/ Abbreviations

ADE	Adverse Device Effect
AE	Adverse Event
b.i.d.	twice per day
BMP	Basic Metabolic Panel
CRF	Case Report Form
CV	Curriculum Vitae
GCP	Good Clinical Practices
ICF	Informed Consent Form
IFU	Instructions for Use
IRB	Investigational Review Board
SAE	Serious Adverse Event
q.d.	once per day
AT	Aspiration Therapy
ASPIRE	Aspire Bariatrics, Inc.
PEG	Percutaneous Endoscopic Gastrostomy
DEXA	Dual Energy X-Ray Absorptiometry

Table of Contents

PROTO	COL SIGNATURE PAGE (SPONSOR)	ii
PROTO	COL SIGNATURE PAGE (INVESTIGATOR)	iii
SYNOP	SIS of PATHWAY STUDY	iv
Table 1:	Schedule of Assessments, Year 1-AT Group	vi
Table 2:	Schedule of Assessments, Years 2-5-AT Group	vii
Table 3:	Schedule of Assessments, Control Group	viii
Table of	Acronyms/ Abbreviations	ix
Table of	Contents	x
Table of	Appendices	xiii
1.0	Introduction	1
1.1	Non-Surgical Treatments (Medical Therapy)	2
1.2	Bariatric Surgery	3
1.2.1	Roux-en-Y Gastric Bypass (GBP)	4
1.2.2	Laparoscopic adjustable gastric banding (LAGB)	4
1.2.3	Sleeve gastrectomy	5
1.3	$Aspire Assist ^{{\scriptscriptstyle TM}} \ and \ Aspiration \ The rapy$	
1.3.1	Percutaneous Endoscopic Gastrostomy	
1.3.3	,	
1.3.4	1 1	
1.3.4	.1 Principles of Operation	12
1.3.4	.2 Training	13
2.0	Study Objective	14
2.1	Primary Efficacy Endpoints (52-week)	14
2.2	Secondary Efficacy Endpoints (52-week)	14
2.3	Safety Outcomes	15
3.0	Study Design	15
4.0	Study Population & Recruitment	16
4.1	Inclusion Criteria	17
4.2	Exclusion Criteria	17
5.0	Study Procedures	19
5 1	Scrooning	10

5.2	Randomization	20
5.3 5.3.	Control Group	
5.3.	2 Pregnancy	23
5.4	Treatment Group (AspireAssist plus Lifestyle Therapy)	
5.4.		
5.4.		
5.4.	1 1	
5.4.	,	
5.4.	· 1	
5.4.		
5.4.		28

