5.5.9 Lifestyle Therapy

The behavioral weight loss program (see **Appendix C**) is a 10-session program delivered individually or in a group to each research subject during the first 52-weeks and includes nutritional, physical activity, and behavioral education topics. AT and Control Subjects are instructed to have a balanced 300 and 600 kcal-deficit diet, respectively. Initial daily energy requirements can be estimated by using the Mifflin-St Jeor equations⁵⁵ to estimate resting energy expenditure in men and women (see below) multiplied by an activity factor of 1.4:

```
Men: Resting Energy Expenditure = (10 x weight in kg) + (6.25 x height in cm) - (5 x age in yrs) + 5

Women: Resting Energy Expenditure =
```

(10 x weight in kg) + (6.25 x height in cm) - (5 x age in yrs) - 161

Subjects are also instructed to establish a structured eating plan, which involves eating three meals a day, eating slowly and chewing food well, drinking a minimum of 500 mls of non-caloric fluid with each meal and at least 2000 mls of fluid per day (including the fluid consumed at meals, and limiting snacking between meals. Physical activity topics include the health benefits of physical activity and strategies for increasing lifestyle activity. The behavioral program emphasizes strategies of self-monitoring and goal-setting, and includes problem-solving, dealing with high-risk situations / cues for unhealthy eating, and stress management.

These Lifestyle Therapy sessions will be given individually during the same visit as the Medical & Study visits or regularly in group sessions.

If a subject in either intervention group is struggling with adherence or

compliance to the therapy, an individual session may be arranged between the subject and a behavioral consultant or another subject from their intervention group who has been successful with the therapy. Meetings will be considered and arranged on an individual basis with the intention of assisting subjects who may require additional attention to address a particular barrier to success with the study intervention. Any such meetings will only be held if the subject is so willing and will require permission, in advance, from the Sponsor.

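### Serum iron is followed in the AT group but not in Controls, so a fall in iron short of anemia has no randomised comparator and low-iron adverse events are looked for in one arm only

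*Protocol*

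**What the plan says.** **The risk.** Protocol section 7.1.3 states: "The nutritional and metabolic risks related to Aspiration Therapy include hypokalemia, and iron (Fe) deficiency anemia". It reports a signal from earlier work: "Serum Fe decreased in several subjects treated with Aspiration Therapy in the Feasibility Study". It says the fall went with lower hemoglobin and, in a few subjects, anemia. Among the possible mechanisms it lists reduced intake and aspiration of iron with the meal, increased menstruation during weight loss, and that "adherence with a low calorie diet and weight loss itself is associated with a decline in serum Fe".

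**The diets.** Section 5.5.9: "AT and Control Subjects are instructed to have a balanced 300 and 600 kcal-deficit diet, respectively". Both arms therefore restrict energy.

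**The schedules.** In "Table 1: Schedule of Assessments, Year 1-AT Group", serum iron is marked at screening and weeks 14, 28 and 52. In "Table 3: Schedule of Assessments, Control Group", it is marked at screening only. Vitamin D 25-OH is marked at screening and week 52 for AT, and at screening only for Controls. The row "Hemoglobin & hematocrit" (weeks 14 and 28) and the CBC row (screening and week 52) are the same in both tables.

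**Adverse events.** Section 7.3.1 counts medically important abnormal test results as adverse events. Section 8.4 compares the number of subjects with at least one adverse event between arms by Fisher's exact test and also tabulates event counts.

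**The concern.** Demonstrating safety is part of the study objective (section 2.0). The protocol has an earlier signal on serum iron, names dieting and weight loss as a rival explanation, and randomises subjects to a diet-only arm. It then does not measure iron in that arm after screening.

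Two things follow.

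- If iron falls in AT without anemia, the trial has no concurrent estimate of how far it would have fallen under lifestyle therapy alone. The analysis cannot repair this later, because the data will not have been collected.
- A low iron value can be found by scheduled testing after screening in AT only. Where such a value is recorded as an adverse event, the AT count rises through closer looking, not necessarily through more harm.

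**Working it through.** **Step 1: reproduce the printed row totals.** Marks counted in each row against the visit columns:

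| Row, first 52 weeks | AT (Table 1) | Control (Table 3) |
|---|---|---|
| Serum iron | screening, weeks 14, 28, 52; printed total 4 | screening; printed total 1 |
| Vitamin D 25-OH | screening, week 52; printed total 2 | screening; printed total 1 |
| Hemoglobin and hematocrit | weeks 14, 28; printed total 2 | weeks 14, 28; printed total 2 |
| CBC | screening, week 52; printed total 2 | screening, week 52; printed total 2 |

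Every count agrees with its printed total, so the asymmetry does not depend on how the columns were read from the PDF.

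**Step 2: measurements after screening.**

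- Serum iron: AT 4 − 1 = 3; Control 1 − 1 = 0.
- Vitamin D: AT 2 − 1 = 1; Control 1 − 1 = 0.
- Hemoglobin (either row): AT 2 + 1 = 3; Control 2 + 1 = 3.

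A between-arm comparison of change therefore exists for hemoglobin at weeks 14, 28 and 52, and at no time for iron or vitamin D.

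**Step 3: is Control blood already drawn?** Yes. Table 3 schedules, among others, hemoglobin/hematocrit and hemoglobin A1C at week 14; the metabolic panel, lipids and hemoglobin A1C at week 28; and the metabolic panel, CBC, lipids and hemoglobin A1C at week 52. Section 5.9 sends all blood to one central laboratory.

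**Step 4: precision if Control iron were added.** Inputs: 117 AT and 58 Control (section 8.1.1); drop-out of 10% in AT and 20% in Controls (section 8.1.2); 5% significance level (section 8.2), taken here as two-sided. The protocol gives no SD for serum iron, so results are in units of the SD of the change, assumed equal in both arms.

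- Completers: 117 × 0.90 = 105.3, taken as 105; 58 × 0.80 = 46.4, taken as 46.
- Standard error: √(1/105 + 1/46) = 0.177 SD.
- 95% half-width: 1.96 × 0.177 = 0.35 SD.
- Detectable difference: (1.96 + 0.84) × 0.177 = 0.50 SD at 80% power; (1.96 + 1.28) × 0.177 = 0.57 SD at 90%.
- With no drop-out (117 v 58): standard error 0.161 SD, half-width 0.32 SD, detectable difference 0.45 SD at 80% power and 0.52 SD at 90%.

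**Step 5: cost.** 58 Controls × 3 visits = 174 iron assays at most. Week-52 vitamin D would add at most 58.

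**The case against.** The case on the other side is substantial, and most of it narrows the point.

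- **The named risk is anemia, and anemia is comparable.** Hemoglobin is scheduled identically in both arms at weeks 14, 28 and 52, and the CBC includes red-cell indices. This stands. A reader might infer from the iron rows that the iron-related risk has no randomised comparison at all; the tables do not support that. What remains is a fall in iron that stops short of anemia. Iron supplementation may also hide such a fall in the hemoglobin data: section 5.4.4, in the treatment-group part of the protocol, raises it for some women with low hemoglobin.
- **Control sampling would not isolate aspiration.** This stands too. It is tempting to say that Control iron would separate aspiration from dieting. It would not: the prescribed energy deficits differ (300 v 600 kcal), the sample size in section 8.1.1 assumes a 25-point difference in %EWL, and section 7.1.3 attributes part of the decline to weight loss itself. Section 5.3 mentions only a multivitamin and mineral supplement for Controls, so unequal iron supplementation could also blunt the contrast. The result would be an effect of the whole package.
- **Vitamin D.** A reader might extend the argument to it because the schedule shows the same asymmetry. The protocol names neither a vitamin D risk of the therapy nor a dieting effect on vitamin D, so the argument rests on iron.
- **Closer monitoring of the implanted arm is legitimate, and iron is not a listed outcome.** True: sections 2.1 to 2.3 do not list it, and no planned efficacy analysis is broken. But adverse events are a safety outcome and are compared between arms, so unequal detection reaches a planned analysis. Section 5.1 states a historical-control comparison for bone mineral density; nothing similar is stated for iron.
- **The effect on the adverse event test may be small.** A low iron value changes the count of subjects with at least one event only if that subject has no other event, and section 7.1.2 reports that most earlier subjects had some stoma complaint. The tabulated number of events is more exposed than the Fisher test.
- **A half-width in SD units says nothing about clinical relevance.** Correct. It describes the precision that the added comparison would have, not harm done by the present plan.

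**Conclusion.** The point holds in a limited form. After screening, serum iron is scheduled three times in AT and never in Controls, although the protocol treats iron deficiency anemia as a therapy risk and names diet and weight loss as a competing cause of lower iron. A fall in iron short of anemia would therefore have no concurrent randomised comparator, and low-iron laboratory events can be found by scheduled testing in AT only. That bias runs against the device. Its size cannot be computed: the protocol gives no expected rate of low iron, and whether a value is recorded as an event depends on its being judged medically important.

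The documents do not support a wider claim that anemia is not comparable, that the same argument applies to vitamin D, or that Control sampling would yield the effect of aspiration alone.

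The primary endpoints are untouched. This is a cheap improvement to the safety data. The 0.35 SD figure rests on the protocol's drop-out assumptions, a two-sided 5% level and a common SD.

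**What to change.** In Table 3, add serum iron to the Control blood draws at weeks 14, 28 and 52, so that the row matches Table 1 and its total becomes 4. Report the between-arm difference in change from baseline with a 95% confidence interval at each of those weeks, next to the hemoglobin comparison. State that it estimates the effect of the randomised package (aspiration with the AT diet against the Control diet, including any difference in weight loss), not of aspiration alone.

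Week-52 vitamin D in Controls is optional and would serve matched detection only.

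Cost: at most 174 extra iron assays at the central laboratory, plus 58 for vitamin D if added. No new visit, blood draw or procedure is needed. If the schedule is left as it is, the report should say that iron was followed in AT only and should show low-iron events separately, so that they are not read as a between-arm difference.
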